EEG Cap for Identification of Non-Convulsive Status Epilepticus

NCT# 03138876

February 22, 2017

RESEARCH PROTOCOL OUTLINE

Title: EEG Cap Placement for Expedited Identification of Non-Convulsive Status Epilepticus

Principal Investigator: [name] D.O.

Co-Investigators: [name] M.D., [name] M.D., [name] D.O., [name] M.D., [name] M.D., [name] D.O., [name]

Abstract

Altered mental status (AMS) is one of the most common reasons for inpatient neurology consultation. Non-convulsive status epilepticus (NCSE) is frequently a differential diagnosis of the patient with AMS. NCSE becomes more refractory to treatment after one hour of seizure activity, making rapid identification and treatment of NCSE of great clinical importance. Currently, an EEG technician must be called in from home during non-workday hours in order to obtain a stat EEG. We propose the time required for diagnosis of NCSE in our institution can be significantly decreased with rapid placement of an EEG cap by the onsite neurology residents.

A. Specific Aims

1. Utilize EEG cap for rapid assessment of seizure activity in 20 patients with suspected NCSE
2. Rapid EEG review by on-call resident & attending physicians
3. Employ existing standard of care for NCSE evaluation with standard electrodes as soon as technician can apply them (cap to not delay standard of care)
4. Evaluate endpoints for cap vs. standard electrodes of time from consultation to:
 - a. completed EEG
 - b. Diagnosis or exclusion of NCSE

B. Background and Significance

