Status epilepticus is operationally defined as a seizure greater than five minutes in duration or more than one seizure within a five minute period without return to normal baseline mental status. Convulsive status epilepticus is a medical emergency. Status epilepticus is more likely to become refractory to medical therapy when treatment is delayed for over 1 hour (DeLorenzo et al). NCSE is a persistent change in behavior and processes from baseline associated with continuous epileptiform EEG changes, but without major motor signs. Nonconvulsive status epilepticus (NCSE) in a comatose patient cannot be diagnosed without electroencephalography (EEG). A previous study has demonstrated the urgency of rapid identification and treatment of NCSE (Meierkord et al). Hospital neurology programs frequently rely on EEG technologists who are on-call but not onsite to place EEG electrodes that are used for assessment of NCSE. EEG caps allow for more rapid electrode placement and EEG analysis, but there exists ambiguity whether rapidly placed caps are sufficiently accurate to reliably identify NCSE for clinical decision-making. Use of EEG cap (also referred to as EEG headsets) in the inpatient setting by onsite neurology providers, if sufficiently reliable versus standard of care electrode-placement, may allow for more rapid identification of NCSE and associated expedited pharmacological treatment.

C. Study Design, Methods, & Statistics

Study will be of prospective design involving 20 patients evaluated at the Mayo Clinic emergency department or hospital that are referred to neurology for evaluation of mental status changes or suspected seizures.

Review type: minimal risk

Is this an interventional study? Yes No

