At the completion of neurology evaluation, if NCSE is in the differential diagnosis according to institution best practice, then consented participants will undergo placement of a large size, 20-channel EEG cap from Electro-Cap International with a Natus E-2-2520-26 electrode board adapter with initiation of recording. The placement of the EEG cap will be restricted to residents formally trained in its placement by an EEG tech. The EEG-cap is already owned by the Mayo Clinic Neurology department, and therefore we will not require further funds to obtain equipment for this study. This study will only be performed during times when EEG techs are not available onsite for rapid placement of standard 21-channel EEG electrodes, such as during night-call shifts. We will not bill for the EEG cap placement, only the subsequent standard EEG protocol which will be followed after the EEG-cap placement.

Prior to placement of EEG cap, evaluating staff member will request stat standard-electrode EEG. We will record time from neurology consultation request to placement of EEG cap as well as time from consultation request to obtaining a standard EEG. We will also record time to confirmation or exclusion of NCSE. Initial diagnosis or exclusion of NCSE will be performed by on call resident, if they received prior training regarding EEG cap placement, and attending. Secondary quality assessment will be performed by two independent EEG interpreters blinded to clinical history. Secondary assessment will be qualified as acceptable or unacceptable interpretation based on whether greater or less than 50% of the recording is judged interpretable. Secondary assessment will also include interpretation of NCSE by a third independent reader if there is disagreement between first two. The number of patients excluded from the study will also be recorded, including the reason for exclusion.

Specific data points for statistical analysis include:

- Time of consultation
- Time of standard-electrode EEG order
- Time that 10 minutes of EEG have been completed (for both cap & standard-electrodes)
- Time that 20 minutes of EEG have been completed (for both cap & standard-electrodes)
- Time of diagnosis or exclusion of NCSE

Primary outcome measure: time from stat EEG order to diagnosis or exclusion of NCSE

Secondary outcome measures include:

- Overall quality of cap recordings as operationalized by:
 - Aforementioned >50% interpretability

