 - Concordance between cap & standard-electrode diagnostic assessments
- comparison of diagnostic assessments/concordance between 10 and 20 minute captures

Statistical methodology: chi-square and Student T-test will be employed to compare categorical variables.

Data storage and PHI: Initial data collection will be to a password-protected Excel spreadsheet that is only accessible by the study authors. No PHI will be collected, but a unique identifying number will be used to initially distinguish between patients. Data will then be aggregated for statistical analysis. The final paper will only include patient data in aggregate form.

D. Preliminary Studies/Progress Report

EEG is the only definitive way to diagnose NCSE. Although useful, standard surface EEG can be a cumbersome, complex and time-consuming process, all of which can limit its applicability in emergent time-sensitive clinical situations and rural areas without available technology, financial resources or neurophysiologic expertise. EEG headsets, caps or “dry EEG” have been developed and have become commercially available over the past few decades and have been used in multiple brain computer interface (BCI) studies, evoked potentials and biofeedback (Halford, et al, Slater et al). This novel technology does not require measurement of relative electrode differences by EEG technologists or pose increased risk for skin abrasions. Disadvantages EEG caps do exist which may affect its clinical suitability, including movement artifact, sweat artifact and increased weight of the system (Halford, et al).

Some studies have investigated the time differences and validity of EEG headsets versus standard EEG recordings in various clinical scenarios. For instance, a study demonstrated that application of an EEG caps in comparison to a standard EEG was performed over 15 minutes faster, with 87% of the EEG being interpreted as technically adequate. In addition, patients preferred the EEG caps over the standard EEG (Halford, et al). The EEG headset recordings were also felt to be adequate in identifying status epilepticus and were significantly faster to set up (Slater et al). “Light” EEG has also been shown to be comparable to standard EEG in detecting findings suggestive of hepatic encephalopathy, but with higher proportion of light EEG samples being discarded due to artifact (Schiff et al).

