Given the nature of the project aimed at expeditiously identifying NCSE the following details will be verbally provided to health care proxies prior to placement of the EEG cap:

- The study involves assessing patient brain waves with an experimental EEG cap to attempt to diagnose and treat seizures that do not produce convulsive movements, but can alter mental status.

- The cap could identify seizures before the normal method of analyzing brain waves will be performed, which could potentially allow for earlier treatment.
- There is minimal risk, with main risk being that cap may be inaccurate and might be misinterpreted. The risk of misdiagnoses, leading to inappropriate diagnosis and treatment is likely small, but exact data is not available.
- The normal method of analyzing brain waves will be used either way as fast as possible
- Do not feel obligated to consent if you prefer for our typical protocol to be followed. The patient's overall care, outside of the context of this study, will not change based on your decision.
- If you would like some time to think about this decision, I will attempt to return at a time of your choosing.

G. Risks and benefits:

This study is considered minimal risk given the only deviation from standard of care involves application of EEG cap prior to standard of electrodes. To the extent that cap electrodes might be misinterpreted due to theoretically poorer quality risks include:

- Misinterpretation of EEG so as to miss seizure activity, which would not affect time to treatment, given we will still be following and giving priority to our standard protocol.
- Misinterpretation of EEG so as to diagnose non-seizure activity as epileptiform, which is unlikely as attendings will avoid diagnosing NCSE if there is any uncertainty in the EEG.

1. Procedures protecting against or minimizing potential risks:
 - a. Patients will be evaluated by neurology residents or faculty members
 - b. EEG cap will be applied by neurology staff and cleaned between each use
 - c. Electronic data will be stored in a password-protected Excel spreadsheet that contains no PHI
 - d. Regular EEG protocol will be followed in addition to EEG cap placement. Standard electrode placement will be given priority in the event EEG technician is available before EEG cap is placed. There will be no deviation from the current standard of care.
2. Future benefits and importance to the participants and others:

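### The primary time outcome does not require the cap's call to be correct, so the time saved can be overstated when cap and standard EEG disagree

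*Combined protocol and SAP*

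**What the plan says.** Section C of the combined protocol and SAP gives "Primary outcome measure: time from stat EEG order to diagnosis or exclusion of NCSE". The call is made in real time: "Initial diagnosis or exclusion of NCSE will be performed by on call resident", together with the attending. Blinded readers come in only as a secondary quality assessment.

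The intended contrast is between devices. Aim 4 in section A reads "Evaluate endpoints for cap vs. standard electrodes of time from consultation to" a completed EEG and a decision on NCSE. The end of section D also plans to compare the two methods on the interval from order to interpretation.

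The list of data points in section C marks the 10- and 20-minute recording times as collected for both devices. The end point of the primary outcome is a single line, "Time of diagnosis or exclusion of NCSE", with no such mark.

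Accuracy appears as a secondary outcome, "Concordance between cap & standard-electrode diagnostic assessments". Nothing links it to the primary time.

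Section G says of a seizure missed on the cap that the error is one "which would not affect time to treatment, given we will still be following and giving priority to our standard protocol". The justification of risks later in section G adds that such a seizure would have gone undetected until standard electrodes were applied in any case. Section B says of accuracy that "there exists ambiguity whether rapidly placed caps are sufficiently accurate to reliably identify NCSE for clinical decision-making".

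**The concern.** The abstract's hypothesis is that the cap shortens the time needed to diagnose NCSE. An outcome that stops at any call, right or wrong, measures time to a decision, which is not the same thing. If the resident and attending exclude NCSE on the cap and the standard EEG then shows it, the patient's correct diagnosis arrives with the standard EEG. By the protocol's own account nothing was gained, but a per-device comparison of decision times would enter that patient as a saving.

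The bias runs one way, in favour of the cap, and it falls mainly on the patients for whom speed matters most, those who have NCSE. A separate concordance figure would show that errors occurred. It would not show how much of the reported saving came from them.

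**Working it through.** The plan states no expected saving, no cap error rate and no basis for its 20 patients, so there is no figure of its own to reproduce. The check is algebraic, with assumed rates.

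**Inputs**
- From the documents: 20 patients (Aim 1); a call of either kind ends the clock (section C); a miss on the cap gains no time (section G).
- Assumed: the share d of cap calls that are wrong; NCSE prevalence p; cap sensitivity s.
- For illustration only: a saving of 15 minutes. Section D reports a difference of more than 15 minutes in a cited headset study, but for application time, not time to diagnosis.

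**Step 1. Saving credited.** For one patient let C be the cap decision time and S the standard-electrode decision time. The credited saving is S − C. Aim 4 starts the clock at consultation and the primary outcome at the EEG order. Each start is common to both devices within a patient, so it cancels in S − C.

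**Step 2. Saving to a correct call.** If the standard EEG confirms the cap, the saving is S − C. If it contradicts the cap, the first correct call comes at S and the saving is 0. Section G supports this for missed seizures. For a wrong positive call it is my extension by the same logic.

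**Step 3. Mean overstatement.** Let G be the mean credited saving. If being wrong is unrelated to the time saved, the mean saving to a correct call is G(1−d), and the overstatement factor is G / [G(1−d)] = 1/(1−d). The factor does not depend on G. The chance of at least one wrong call in 20 is 1 − (1−d)^20.

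| d (assumed) | Factor 1/(1−d) | 15 min becomes | Chance of ≥1 wrong call in 20 |
|---|---|---|---|
| 0% | 1.00 | 15.0 | 0% |
| 5% | 1.05 | 14.25 | 64% |
| 10% | 1.11 | 13.5 | 88% |
| 20% | 1.25 | 12.0 | 99% |

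**Step 4. Misses only.** Counting only false exclusions, d = p(1−s).
- p = 10%, s = 90%: d = 0.10 × 0.10 = 1%, factor 1.01.
- p = 30%, s = 50%: d = 0.30 × 0.50 = 15%, factor 1.18.

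Among patients who have NCSE the error share is 1−s, so the factor is 1/s: 1.11 at s = 90%, 1.33 at 75%, 2.0 at 50%. Because p is below 1, p(1−s) is always smaller than 1−s, so the effect of misses is larger in the NCSE group than overall.

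**The case against.** **The documents set no rule that credits wrong calls.** This stands. The decision time is listed once and is not marked per device, so a reader who infers that the plan awards the cap its full saving for wrong calls is reading silence as a rule. A single final diagnosis time would not credit the cap. But every patient is meant to have both recordings and there is no separate control group, so one time per patient would leave no cap-versus-standard comparison, which Aim 4 requires. Either way, the end time needs defining.

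**False exclusion need not be the likelier error.** Section G says "attendings will avoid diagnosing NCSE if there is any uncertainty in the EEG". It is tempting to infer that uncertain readings become exclusions. The text does not say so: withholding a diagnosis may mean no decision until the standard EEG, which is a different problem. What remains is that the stated safeguard addresses wrong positives only.

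**Section G speaks of time to treatment, not time to diagnosis.** This is correct, and it does not say that the standard EEG alone settles the matter. The inference is still reasonable, because a seizure missed on the cap is not diagnosed by the cap.

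**A two-fold overstatement is not supported.** Section D cites 2 of 4 status epilepticus cases found with forehead electrodes. That is another device, its misses were attributed to posterior abnormalities, and the exact 95% interval for 2/4 is 6.8% to 93.2%. Section D also cites headset recordings judged adequate for identifying status epilepticus.

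**Accuracy is already assessed.** Concordance is planned, with blinded readers and a third to resolve disagreement. A device that excluded NCSE in everyone would be exposed by discordance in every confirmed case. Nor does a positive primary result become uninformative: at d = 25%, three-quarters of the saving would remain. Presenting speed and accuracy side by side is a legitimate choice for 20 patients. It still leaves the saving itself uncorrected.

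**A blanket zero for discordant pairs would add bias.** This stands too. NCSE correctly found on the cap and treated before the standard EEG could look discordant, so such a rule would penalise a success.

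**Conclusion.** The concern holds in a conditional form. The primary outcome does not ask whether the call was correct, and the plan does not say which time applies when the devices disagree. On the per-device comparison that Aim 4 and section D imply, the mean saving can be overstated by 1/(1−d). The overstatement is nil with full concordance, 5% at d = 5% and 11% at d = 10%. It ranges from about 1% to 18% in the misses-only scenarios, and is larger among patients with confirmed NCSE.

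This rests on decision times being compared per device, on error being unrelated to time saved, and on a contradicted call saving no time. All error rates, prevalences and sensitivities are assumed, so the documents do not show that the saving *is* overstated, only that it can be. They do not support a conclusion that a favourable result would be empty. The gap is worth closing because the bias favours the cap and closing it costs little.

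**What to change.** 1. Record the decision time separately for the cap and for the standard electrodes.
2. Report the crude saving together with a pre-specified concordance-corrected saving. In the corrected version, a cap call contradicted by the standard EEG takes the standard-electrode decision time.
3. Show the numbers of wrong exclusions and wrong diagnoses beside both, and give the saving separately for patients whose NCSE is confirmed.
4. Where anti-seizure treatment was given between the two recordings, do not automatically count a cap-positive, standard-negative pair as a cap error. Judge it by the blinded readers' interpretation of the cap recording, or show it separately.
5. Base any claim of faster diagnosis on both results.

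The cost is modest. Both diagnoses are already needed for concordance. The additions are a decision time for each device, a note of whether treatment fell between the recordings, and a few lines of analysis text. The downside is that the corrected saving will be somewhat less favourable, and some discordance may reflect real EEG change between recordings. Reporting both versions shows how much this matters.

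### Cap-versus-standard concordance has no agreement or accuracy statistic, and chi-square, the only categorical method named, does not measure agreement

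*Combined protocol and SAP*

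**What the plan says.** Section C (Secondary outcome measures) introduces the cap-quality outcome as "Overall quality of cap recordings as operationalized by" two items: the rule that more than half of the recording be interpretable, and "Concordance between cap & standard-electrode diagnostic assessments". A further secondary outcome is "comparison of diagnostic assessments/concordance between 10 and 20 minute captures".

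The analysis plan is one sentence under Statistical methodology in Section C: "chi-square and Student T-test will be employed to compare categorical variables". It is linked to no endpoint. It also assigns the t-test to categorical data, which leaves chi-square as the only categorical method named. Nowhere do the documents mention kappa, percentage agreement with an interval, sensitivity, specificity or McNemar's test, and they set no level of concordance that would be acceptable. The interpretability rule grades recordings, and the third reader settles disputes between readers. Neither measures agreement.

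On the readings, Section C says "Initial diagnosis or exclusion of NCSE will be performed by on call resident, if they received prior training regarding EEG cap placement, and attending", and then "Secondary quality assessment will be performed by two independent EEG interpreters blinded to clinical history". It does not say whether the blinded readers see the standard recordings, or the 10- and 20-minute captures separately.

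On order, Section C refers to billing "only the subsequent standard EEG protocol which will be followed after the EEG-cap placement". The wording for proxies in Section F adds: "The cap could identify seizures before the normal method of analyzing brain waves will be performed, which could potentially allow for earlier treatment".

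**The concern.** Section B says it is unclear whether a quickly placed cap is accurate enough to identify NCSE, and Section D says the study will look into this. Cap-versus-standard concordance is the only listed outcome that plainly compares the two diagnoses, so it carries that question.

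The two diagnoses belong to the same patient. The documents never use the word paired; this follows from the design. For paired yes/no data, the association form of chi-square shows that the readings are related but not in which direction. The unpaired form compares positive rates and ignores which patients were positive. A plain percentage, if used instead, can be made up largely of shared negatives. With no statistic fixed in advance, one table could be reported as a significant association, as no significant difference, or as high concordance, and none of these would show how many cases the cap found.

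**Working it through.** The plan gives no figure to reproduce: 20 patients is stated without an expected agreement, an NCSE rate or a precision target. The check therefore uses assumed tables with N = 20 (the sample size in Section A).

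**Notation.** a = both positive, b = cap only, c = standard only, d = both negative, written a/b/c/d.

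**Formulas.**
- Association chi-square (uncorrected) = N(ad − bc)² / [(a+b)(c+d)(a+c)(b+d)]
- Unpaired chi-square: (a+b)/20 against (a+c)/20, treated as two independent groups of 20
- Raw concordance = (a+d)/N
- Kappa = (po − pe)/(1 − pe), where po is raw concordance and pe = [(a+b)(a+c) + (c+d)(b+d)]/N²
- Sensitivity = a/(a+c); specificity = d/(b+d); exact (Clopper-Pearson) 95% intervals

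**Results.**

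| Table | Raw concordance | Association chi-square | Unpaired p | Exact McNemar p | Kappa |
|---|---|---|---|---|---|
| 10/0/0/10 | 100% | 20.0 | 1.0 | 1.0 (no discordant pairs) | 1 |
| 0/10/10/0 | 0% | 20.0 | 1.0 | 1.0 | −1 |
| 0/4/4/12 | 60% | 1.25 (p = 0.26) | 1.0 | 1.0 | −0.25 |
| 2/0/2/16 | 90% | 8.89 (p = 0.003) | 0.38 | 0.5 | 0.62 |

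**Rows 1 and 2.** Both give 20 × 100² / (10 × 10 × 10 × 10) = 20.0. Squaring removes the sign of ad − bc, so complete agreement and complete disagreement look the same.

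**Row 3.** Each method calls 4 of 20 positive, but never the same patient. The unpaired comparison sees no difference.

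**Row 4 (cap misses 2 of an assumed 4 cases, no false positives).**
- Association: 20 × (2×16 − 0)² / (2 × 18 × 4 × 16) = 20480/2304 = 8.89, p = 0.003
- Unpaired: 2/20 v 4/20, chi-square = 40 × (2×16 − 18×4)² / (20 × 20 × 6 × 34) = 64000/81600 = 0.78, p = 0.38
- Raw concordance: 18/20 = 90%, of which 16 of the 18 agreements are shared negatives
- Sensitivity: 2/4 = 50%, exact 95% CI 7% to 93%
- Smallest expected cell: 2 × 4/20 = 0.4, so the chi-square approximation is itself doubtful

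**How far this depends on the NCSE rate.** With half of the cases missed and no false positives:

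| Positives by standard EEG | Raw concordance | Unpaired p | Exact McNemar p |
|---|---|---|---|
| 2 (10%) | 95% | 0.55 | 1.0 |
| 4 (20%) | 90% | 0.38 | 0.5 |
| 6 (30%) | 85% | 0.26 | 0.25 |
| 8 (40%) | 80% | 0.17 | 0.125 |
| 12 (60%) | 70% | 0.057 | 0.031 |
| 14 (70%) | 65% | 0.027 | 0.016 |

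The misses are hidden when NCSE is uncommon among suspected cases and become visible when it is common.

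**Kappa and timing.** Suppose the cap is right in 4 cases, but 2 have resolved by the later standard EEG (2/2/0/16). Then po = 18/20 = 0.90, pe = (4×2 + 16×18)/400 = 0.74, and kappa = 0.16/0.26 = 0.62. That equals the kappa for a cap that missed 2 of 4. Kappa alone does not separate the two situations; the table does.

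**Precision after the fix.** If every case is detected, the lower 95% limit is 0.025^(1/n): 16% for 2/2, 40% for 4/4, 54% for 6/6.

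**The case against.** The strongest reply has three parts.

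- **The chi-square sentence is general.** It is not attached to concordance, and the investigators may intend a simple percentage. This stands: a reader might infer that chi-square is definitely planned for these outcomes, and the documents do not say so. What remains is that no other categorical method is offered, and that a percentage alone would also hide missed cases when NCSE is uncommon.
- **The illustrations are assumed.** This also stands. The documents give no NCSE rate. A reader might take the 2-of-4 result in Section D as a forecast of this cap's sensitivity, but it came from forehead electrodes and does not predict a 20-channel cap. The identity of rows 1 and 2, however, needs no assumption about the NCSE rate or miss rate: it shows what the test cannot distinguish.
- **These are secondary outcomes in 20 patients, and no statistic would settle accuracy.** The point about precision is correct. It is a reason to show the interval rather than omit it.

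Two limits on the remedy also hold. Sections C and H commit to aggregate reporting, so discordant patients should be counted, not listed one by one. The 10- versus 20-minute outcome can be read in two ways: agreement between captures of one recording, or cap-standard concordance at each duration. The first needs a separate diagnosis per capture, and the plan does not clearly provide one.

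**Conclusion.** The concern holds as an omission with a practical consequence. The plan names no statistic that measures agreement or accuracy, and the one categorical method it does name cannot answer the question raised in Sections B and D. In the assumed example of 4 cases, a cap that misses half of them yields 90% concordance, association p = 0.003 and unpaired p = 0.38, against a sensitivity interval of 7% to 93%. This rests on pairing inferred from the design and on an assumed NCSE count and miss rate.

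Three stronger readings are not supported. The primary outcome and the time endpoints of Aim 4 are not affected. Missed cases would not be hidden at every NCSE rate. And a cap-positive, standard-negative pair is not necessarily a false positive, because the standard EEG comes later, possibly after treatment.

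**What to change.** In Section C, Statistical methodology:

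1. **Cap versus standard.** In place of chi-square, specify the paired 2x2 table, with sensitivity and specificity against the standard EEG and exact 95% intervals. Kappa is optional. Use exact McNemar only to describe the direction of disagreement.
2. **Source of the diagnoses.** State which readings are used, whether they cover both recordings, and whether they are blinded. Label the initial resident and attending diagnoses as unblinded if those are used.
3. **Aggregate counts.** Report the numbers of incomplete pairs, uninterpretable cap recordings and cap-positive/standard-negative pairs, with a note that the standard EEG is later. Incomplete pairs can arise when the technician is available first (Section G) or the study stops because the patient regains the ability to interact (Section F).
4. **10 versus 20 minutes.** State which comparison is meant. Where a diagnosis per capture exists, report positive agreement, 2a/(2a+b+c), and negative agreement, 2d/(2d+b+c), with b and c as the two discordant cells.
5. **Interpretation.** Base any statement about identifying NCSE on the sensitivity interval, not on overall concordance.

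Cost: for cap versus standard, wording and a few lines of code, with no new patients or recordings. A diagnosis per capture, if not already planned, would be extra reader work, so item 4 applies only where one exists. The downside is wide intervals: even 4 of 4 detected gives a lower limit of 40%, so the study can describe the cap's accuracy but cannot establish that it is reliable.

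### The 10- versus 20-minute concordance outcome has no suitable analysis (chi-square does not measure paired agreement) and no stated reading procedure, so the result could reassure wrongly and may be biased upward by an unknown amount.

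*Combined protocol and SAP*

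**What the plan says.** All the relevant text is in section C (Study Design, Methods, & Statistics).

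- **Outcome.** The last secondary outcome is "comparison of diagnostic assessments/concordance between 10 and 20 minute captures". No agreement statistic, target or margin is attached, and the type of recording (cap, standard electrodes or both) is not given.
- **Captures.** The data points include "Time that 10 minutes of EEG have been completed (for both cap & standard-electrodes" and "Time that 20 minutes of EEG have been completed (for both cap & standard-electrodes". These read as two time marks on one recording per modality. Nesting is implied, not stated.
- **Diagnosis.** One item is listed, "Time of diagnosis or exclusion of NCSE". It is not split by capture length.
- **Readers.** "Initial diagnosis or exclusion of NCSE will be performed by on call resident, if they received prior training regarding EEG cap placement, and attending". Then, "Secondary quality assessment will be performed by two independent EEG interpreters blinded to clinical history", and "Secondary assessment will also include interpretation of NCSE by a third independent reader if there is disagreement between first two". No reader is tied to a capture length, and the only masking stated is to clinical history.
- **Analysis.** A single sentence names chi-square and Student's t-test for all comparisons of categorical variables. No paired or agreement method appears.
- **Size.** "Study will be of prospective design involving 20 patients".

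**The concern.** Asking whether the first 10 minutes gives the same answer as the full 20 is sensible, and one recording per patient is the natural place to ask it. Two things are missing.

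The first is a suitable analysis. The useful result is how many diagnoses change between 10 and 20 minutes, and in which direction. Chi-square does not give that. Two reads of the same recording will nearly always be associated, so a significant association says little. A non-significant difference in proportions between two groups treated as separate says little either, at this sample size.

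The second is a reading procedure. A reader who has already seen all 20 minutes can assign the 10-minute result with hindsight. A reader who has committed at 10 minutes can repeat that answer at 20. Both raise agreement. The protocol neither rules these out nor says that they occur.

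At stake is how far the 10- versus 20-minute result can be believed. A missed positive at 10 minutes is the event that matters most, and the present plan could leave it out of sight.

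**Working it through.** The plan gives no expected concordance, alpha, power or margin for this outcome, so there is no figure to reproduce. The example below is hypothetical and is used only to see how the named method behaves.

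**Inputs**
- N = 20, from section C.
- Assumed: 6 patients positive for NCSE at 20 minutes, 3 of them called negative at 10 minutes, no other changes.

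| | 20 min positive | 20 min negative | Total |
|---|---|---|---|
| 10 min positive | 3 | 0 | 3 |
| 10 min negative | 3 | 14 | 17 |
| Total | 6 | 14 | 20 |

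**Chi-square on the paired table** (no continuity correction)

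N(ad − bc)² / (product of the four margins) = 20 × (3 × 14 − 0 × 3)² / (3 × 17 × 6 × 14) = 35,280 / 4,284 = 8.24, p = 0.004. Fisher's exact p = 0.018. The association is significant although half the positives were missed.

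**Chi-square with the reads treated as separate groups** (3/20 against 6/20)

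40 × (3 × 14 − 17 × 6)² / (20 × 20 × 9 × 31) = 144,000 / 111,600 = 1.29, p = 0.26. This would be reported as no difference.

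**Direct description of the same data**
- Diagnoses changed: 3/20 = 15%, exact (Clopper-Pearson) 95% CI 3.2% to 37.9%. All three go from negative to positive.
- Positive agreement relative to the 20-minute read: 3/6 = 50%, exact 95% CI 11.8% to 88.2%.
- Negative agreement: 14/14, exact 95% lower limit 0.025^(1/14) = 76.8%.

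**Why overall agreement alone is not enough**

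Negatives dominate it. With an assumed prevalence of 10%, only 50% of positives caught at 10 minutes and 5% false positives at 10 minutes, overall agreement is 0.10 × 0.50 + 0.90 × 0.95 = 0.905.

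**What 20 patients can show at best**
- No change in 20: upper 95% limit 1 − 0.025^(1/20) = 16.8%.
- All positives agree: lower limit 0.025^(1/m), which is 15.8% for m = 2 positives, 39.8% for m = 4 and 54.1% for m = 6.

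**Direction of the reading bias**

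Let d be the discordance that separate, uninfluenced reads would show, and c the share of those discordances that a reader brings into line through hindsight or anchoring. Observed agreement is 1 − (1 − c) × d. At c = 0 there is no bias; at c = 1 agreement is 100% whatever d is. For any c above 0 (with d above 0) the bias is upward. The documents give neither c nor d, so no size can be put on it.

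**The case against.** Four points can fairly be made against this.

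*The protocol is silent, not wrong, about the reads.* This stands. A reader might infer that the same people read both captures, that the 10-minute read is not locked, and that concordance is therefore inflated. The documents say none of this. They leave the procedure unspecified, and the most that follows is that concordance may be biased upward.

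*Nesting is no flaw, and nothing here proves the outcome useless.* This also stands. A reader might infer that because the 10-minute capture is the first half of the 20-minute one, the comparison cannot show that 10 minutes is enough. Locked or masked reads of nested segments could inform that question. Nor does the protocol state sufficiency of 10 minutes as a goal; the Specific Aims concern cap against standard electrodes. The small sample and the likely few positives limit any such conclusion however the reads are done.

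*Chi-square is not assigned to this outcome by name.* True: one general sentence covers everything. But it is the only named method that suits a categorical outcome, and nothing in the plan offers an alternative for paired reads.

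*Locking is only a partial remedy and could disturb clinical work.* Partly right. Locking the 10-minute read prevents hindsight on that read but does not stop the same reader repeating the answer at 20 minutes. The on-call read, whose timing feeds the primary outcome, should not be touched.

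**Conclusion.** The concern holds as a gap in analysis and procedure for one secondary outcome. Its firmest part is the analysis: chi-square does not measure agreement between paired reads, and in the example it can look reassuring at p = 0.004 or at p = 0.26 while half the positives are missed. That rests on the general methods sentence applying to this outcome and on the captures being nested, which the data points strongly suggest.

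The reading procedure is unspecified, so upward bias is possible and its size is unknown. The conclusion does not depend on any assumed amount of bias. Agreement with the 20-minute read would in any case show sufficiency relative to 20 minutes, not accuracy for NCSE. The point is minor and inexpensive to settle; it does not affect the primary outcome.

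**What to change.** 1. **Analysis.** For this outcome, replace chi-square with the number and direction of diagnoses that change from 10 to 20 minutes, with exact 95% CIs, plus positive and negative agreement with exact CIs. State whether the outcome covers cap recordings, standard recordings or both, and report each separately. State beside the result that 0/20 changed still leaves an upper limit of 16.8%.
2. **Reading.** Specify who reads each capture and in what order. In the existing secondary blinded read only, record and lock an assessment of the first 10 minutes before the full recording is released. Have the third reader follow the same order where adjudication is needed. Leave the on-call diagnostic read as it is.
3. **Reporting.** Say as a limitation that locking prevents hindsight on the 10-minute read but does not fully remove anchoring of the 20-minute read.

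Cost: a small amount of extra reading work for the existing readers. No further patients, recordings or readers are needed.
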